QMT= Quantitative Muscle Testing
RM = Magnetic Resonance
RX= radiography
VIT D= Vitamin D
VR= Residual Volume

3. Responsibility (role of the study promoter and of researchers)

Main researcher: [name] Collaborators: [name], graduated with [name] and now attending the first year of school in medical genetics at the Fondazione IRCCS Cà Granda, Ospedale Maggiore Policlinico. She will collect clinical charts and report clinical data to analyze in a excel file that will be used for the statistics. [name], Director of the Neuromuscular and rare Disease Unit

4. Emendamenti ed altre modifiche al protocollo Not relevant.

5. Timelines Planning: start of data collection: June 2020. End of data collection: September 2020
Final report: December 2020

6. Rational and background

LGMD2E is a rare type of a hereditary muscular dystrophy transmitted in an autosomic recessive manner. This disease is determined by the presence of mutations involving the Beta Sarcoglycan gene, coding for a protein which is involved in the stabilization of the glycoprotein complex

associated to dystrophin (1). The main role of beta Sarcoglycan only partly explains the severity of the clinical phenotype reported in these patients compared with other LGMD (2). LGMD 2E debuts in early childhood, involving skeletal muscles with a progressive centripetal trend that in last stages affects also respiratory and cardiac muscles (3). The early onset and the severity of the disease affecting cardiopulmonary apparatus, make this disease very close to the more famous and studied Duchenne Muscular Dystrophy (4). More than 60% of LGMD 2E patients suffer from heart failure (5), not less common is the involvement of respiratory system which insufficiency represents the main cause of death in these patients (6). Unfortunately, because of its rareness, literature is poor of data about this disorder and no natural history study have ever been reported until now. Lacking similar studies, therapeutical and clinical management is not easy and often based on studies investigating other subtypes of muscular dystrophies, often more benign.

Furthermore, we have little knowledge about possible genotype-phenotype correlations for this disease (7). We do believe that a natural history study might help us to improve our knowledge of this condition's evolution, leading to the design of specific guidelines for the follow up of these patients, both under the therapeutical and clinical point of view.

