8.2 Setting

Patients followed by the ambulatory of neuromuscular disorders of Centro Dino Ferrari, Padiglione Monteggia of Fondazione IRCCS Ca' Granda Ospedale Maggiore Policlinico (Unit of Neurology), will be recruited during the ordinary follow up routine or will be reached out to participate to this study. Furthermore, thank to the sponsorship of Gruppo familiari beta sarcoglicanopatie (GFB), more patients that are in the network of this association will be reached out from the PI of the study and eventually included. Data will be provided by patients themselves during the visit at the room number 17 of Padiglione Monteggia of Fondazione IRCCS Ca' Granda Ospedale Maggiore Policlinico (Unit of Neurology). If the patients won't be able to move and will be interested in participating to the study a collaborator of the main researcher will reach the patients at his residence to recruit him. Main source of data will be the clinical chart of the patient and all his clinical documents assessing any operation, ascertain, visits performer through the years until this moment. Main centre will be the Fondazione IRCCS Ca' Granda Ospedale Maggiore Policlinico (Unit of Neurology). Data collection will last six months and later data will be studied.

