8.2.2 Inclusion criteria

Will be included only those patients, both adults and minors, that have a genetical diagnosis of LGMD 2E and that will sign the specific informed consent for data management.

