8.2.4 Patient participation

Patients might be asked to give to their physician their clinical charts in order to evaluate the visits and investigations performed through the years, also in other hospitals.

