8.3 Variables

Will be extract from the clinical charts of these patients, after the sign of the informed consent for the data management, only retrospective data (therefore all those data older than the day of the recruiting visit).

These data will be reported in a excel file specifically created. On this file data will be anonymized through a patient identification code that will be decrypted in another separate file. For this file will be considered the following data:

a) Dati anagrafici:

1. Anonymized name
2. Sex
3. Age

Form 2- DIAGNOSIS:

- 1) Age at onset
- a) clinical presentation
- b) clinical progression
- 2) CK at onset
- 3) EMG

4) Biopsy:

- a) Histology
- b) Immunohistochemistry
- c) Western Blot

5) Genetic:

- a) In frame del/dupl
- b) Out of frame del/dupl
- c) Missense
- d) Nonsense

Form 3- CLINICAL DATA AND TREATMENTS:

Hospitalization: Data – Cause – Frequency* Surgery: Data – Complications* Fractures: Data – Frequency – Location* Fell: Data – Frequency* Emergency Room Accesses: Data – Cause*

APPARATUS

Skeletal-Muscle

1) Clinical tests:

NSAA* MFM* QMT* Brook Scale* Egen Klassifikation* Barthel Index* Walton and Gardner* & Medwin GSGC* Grip Strength (quantitative)* Handheld Dynamometry* Performance of the Upper Limb Module for DMD 2.0* 10m Walk: 1- normal, 2- slightly impaired- 3 moderately impaired- 4- impaired- 5 with device - 6 not walking but stands- 7 wheelchair 6MWT* time to rise from the floor* Climb 4 stairs (1 no help - 2 one hand on the leg – 3 two hands on the legs - 4 stand with help -5 Handrail - 6 hardly climbs- 7 Not able). 10m Run

Time to rise from a chair (1 Normal - 2 with difficulties -3* helping with one hand - 4 Helping with two hands - 5 other helps - 6 Impossible). Time to stand from the floor (1 Normal - 2 first rise the pelvis and then one hand on the floor - 3 First rise the pelvis and then two hands on the floor - 4 One hand on the leg - 5 Two hands on the legs - 6 Other help - 7 Impossible).

Neuromuscular evaluation (date): maximal voluntary strength: bilateral knees extension, Isometric contraction test*, bilateral knee flexion, Workspace volume

2) Exams:

CK* Muscular RMN

3) Symptoms:

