8.4 Data sources

Data used to collect variables will include any clinical document provided by patients or available in our hospital thank to the server of the Unit of Neurology. Only official clinical charts will be considered. Clinical outcomes will be defined as the age of loss of ambulation, the age of introduction of cardiological supporting drugs and the age of introduction of respiratory supporting devices/therapies. These ages will be directly obtained from the clinical reports (on report it is reported the age of the patient) of indirectly (according to the data of the report that describes the first introduction of the drug/devices or that firstly reports the loss of the ambulation)

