8.7 Data analysis

Analysis will be performed using generalized linear regression models suitable both for continuous variables both for independent ones. Variables with a nonlinear distribution will be transformed in logarithmic scale before the analysis to be performed. For any analysis data will be divided according to the age of the patient at the moment of the evaluation. Data will be analyzed with linear correlation both compared to the variable age both in bivariate models and multivariate models. Results obtained will be adjusted for confounding factors not related to muscular dystrophy.

Data of included patients will be globally studied and divided in two groups homogeneous for genotype.

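### Age at first cardiac drug and age at first respiratory support depend on treatment practice as well as on disease, and the plan does not secure an adjustment for era

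*Protocol*

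**What the plan says.** **Outcomes.** Section 8.4 reads "Clinical outcomes will be defined as the age of loss of ambulation", followed by "the age of introduction of cardiological supporting drugs and the age of introduction of respiratory supporting devices/therapies". The first is a disease milestone. The other two are the ages at which a treatment or support was started.

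**Calendar window.** Section 8.3 admits "only retrospective data (therefore all those data older than the day of the recruiting visit", which is an upper limit only. Section 8.2 takes documents on "visits performer through the years until this moment", and section 8.2.4 asks for charts "in order to evaluate the visits and investigations performed through the years, also in other hospitals". The ten years in section 8.5 explain how the figure of 33 patients was counted. They do not restrict the data.

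**Patients.** Section 8.2.2: "Will be included only those patients, both adults and minors, that have a genetical diagnosis of LGMD 2E". No age limit is set.

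**Management.** Section 6 says that "therapeutical and clinical management is not easy and often based on studies investigating other subtypes of muscular dystrophies".

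**Analysis.** Section 8.7 divides the data by age at evaluation, splits patients into two genotype groups, and states: "Results obtained will be adjusted for confounding factors not related to muscular dystrophy". Neither that section nor the limitations in section 8.9 mention birth cohort, calendar period or changing practice.

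**The concern.** An age at treatment start reflects two things: how far the disease had advanced, and what clinicians were doing at the time. By the protocol's own account there was no disease-specific guidance that would have held the second constant. If treatment came to be started earlier over the years, patients born earlier would show later start ages than patients born later with the same disease.

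Age as the time axis does not remove this, because two patients evaluated at the same age may have been evaluated decades apart. The adjustment rule is no safeguard either. A change in how the cardiac and respiratory complications of a muscular dystrophy are treated is not clearly a factor unrelated to that dystrophy.

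These two ages feed the correlations with clinical outcomes and between phenotype and genotype (section 8.1.1), and they bear on the secondary objective on cardiopulmonary impairment (section 7). A genotype group that happens to be born earlier could look milder than it is.

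**Working it through.** The protocol has no calculation to reproduce. The 33 is a head count, and no effect size, SD or drift is given. Every drift, gap and SD below is an assumption.

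**1. Can birth year be recovered?** Section 8.3 lists age but no date or year of birth. Section 5 places data collection in June to September 2020. A patient aged *a* at the visit was born in 2020 − *a* or 2019 − *a*, so birth year is known to within one year. Section 8.4 also derives some event ages from report dates, which already requires a birth date. The therapy record in section 8.3 appears to carry a date. The respiratory-support items do not carry one of their own.

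**2. Bias in the genotype comparison without birth year.** Bias ≈ drift per birth year × difference in mean birth year.
- Drift 0.1, gap 5 years: 0.1 × 5 = 0.5 year.
- Drift 0.3, gap 5 years: 0.3 × 5 = 1.5 years.

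In purely descriptive milestone ages, drift alone is enough. Over an assumed 30-year span of birth years, 0.1 × 30 = 3 to 0.3 × 30 = 9 years separate the oldest and youngest patients.

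**3. Scale.** With an assumed residual SD of 6 years and groups of 16 and 17, the standard error of the group difference is 6 × √(1/16 + 1/17) = 2.09 years. A bias of 0.5 to 1.5 years is then 0.24 to 0.72 standard errors. At 80% power the detectable standardized difference is 0.98, that is 0.98 × 6 = 5.9 years.

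**4. Simulation with no true genotype effect and every start observed** (16 v 17 patients, residual SD 6, birth-year SD 10, 4,000 runs per setting):

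| Drift (years earlier per decade) | Gap (years) | Bias, no birth year | False positives, no birth year |
|---|---|---|---|
| 2 | 5 | −1.0 | 7.3% |
| 2 | 10 | −1.9 | 13.4% |
| 4 | 5 | −2.0 | 11.4% |
| 4 | 10 | −3.9 | 31.8% |

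With zero drift, or with no systematic gap, there was no bias and the error rate stayed near 5%. With birth year in the model, bias was within 0.1 year and false positives were 4.7% to 5.4% in all nine settings.

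**5. Truncation.** A start is seen only if it happened before the 2020 visit, so later-born patients can contribute only early ages. This was simulated with *no* change in practice (33 patients, birth years uniform over 1970–2010 or 1980–2010, start age mean 15, 20 or 25, SD 6). Among observed starts, the birth-year slope averaged −0.11 to −0.41 year per birth year. Mean observed age differed by about 2 to 6 years between earlier and later birth cohorts (for example 19.9 v 16.8). Truncation alone therefore imitates the drift assumed in step 2.

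**6. Does the covariate still help under truncation?** In an illustrative simulation with no true genotype effect and a 5-year gap, adding birth year moved the bias from −1.2 to 0.1 year with drift 0.2, and from −0.5 to 0.2 year with no drift. False positives stayed near 5%. When the true difference was 5 years, truncation shrank the estimate to about 4 years with the covariate and 3.7 to 4.8 without it. The covariate removes most of the null bias but does not repair the attenuation.

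**The case against.** - **Birth year is effectively available.** A reader might infer from the variable list that it is not collected and that no adjustment is possible. Step 1 shows otherwise. This stands, and it makes the fix cheap.
- **Adjustment is promised.** A reader might infer that era is left unadjusted. Section 8.7 names no confounders. Era is not itself a feature of the dystrophy, so the wording could cover it, and the covariate list may sit in an analysis plan that is not shown. This stands in part. The protocol does not rule the adjustment out, but its wording does not secure it and can be read as excluding it.
- **No drift is documented.** Section 6 describes a lack of specific guidance. It does not say that start ages changed over time. This stands: the mixing is possible, not shown, and the size rests on assumptions.
- **Comparing observed start ages by birth cohort would mislead.** Step 5 shows a gap with no change in practice at all. This stands and shapes the fix.
- **Disease course is not read from treatment ages alone.** Section 8.3 also lists ejection fraction, ventricular dimensions, respiratory pressures and sleep oximetry, and section 8.9 disclaims reliable conclusions on the impact of therapies. This limits the damage. It does not protect the two outcomes that section 8.4 defines, and the disclaimer does not concern changing practice.

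**Conclusion.** The point holds in a limited form. Two of the three clinical outcomes depend on practice, their calendar window is open at the early end, and the stated adjustment does not secure control for era. Following the plan as written may therefore mix era with disease course in these two ages and in the genotype comparison.

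The documents do not support saying that changes in practice *are* being read as disease differences. In the group comparison, era bias needs both a drift in practice and a birth-year gap between the groups, and neither is documented. Under the assumed 0.1 to 0.3 year per birth year and a 5-year gap, the bias is 0.5 to 1.5 years. That is under one standard error if the residual SD is 6 years. It grows with a larger drift or gap. Age at loss of ambulation is not a treatment start and is outside the point.

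**What to change.** 1. Derive year of birth from age at the 2020 visit or from the key file, and record the calendar year of each milestone. This matters most where section 8.4 lets the age be read directly from a report.
2. Name birth year as a covariate in every model of the two treatment-start ages, including the genotype comparison, so that it does not depend on how the rule in section 8.7 is read.
3. Keep patients who have not reached the milestone, censored at their age at the recruiting visit, in a time-to-event model on the age scale. Censoring age is nearly fixed by birth year, which is a further reason to have birth year in the model.
4. Show any comparison of earlier and later birth cohorts as time-to-event curves, not as means of observed ages.
5. Label both outcomes practice-dependent, add era to section 8.9, and read them beside age at loss of ambulation and the cardiac and respiratory measures already listed in section 8.3.

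The cost is one or two fields, one degree of freedom in about 33 patients, and a time-to-event model for these two outcomes. The birth-year coefficient must not itself be reported as a pure effect of practice.

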8.1.1 Primary endpoints

To describe the natural history of the LGMD 2E

To define of the clinical variables that more strongly relate with the evolution of the disease

To identify any possible correlation between variables

To identify any possible correlation between variables and clinical outcomes

To identify any possible correlation between phenotype and genotype

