8.5 Cohort dimension

Expected cohort dimension is of 33 patients that is the number of patients followed at the Neurological Unit in the last 10 years. Statistical analysis will be based on generalized linear regression models, suitable both for continuous variables both for independent ones. Variables with a nonlinear distribution will be used only in logarithmic scale. Only data corresponding to yearly visit (at least two data in two years) will be used for the linear correlation analysis and in multivariate correlation models. Furthermore, to verify the accuracy of clinical variables in

describing the evolution of the dystrophy, variables will be coupled and compared by a bivariate analysis.

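### Where a milestone age is dated indirectly, the first report of the event is only an upper bound, so the age (chiefly at loss of ambulation) can only be late

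*Protocol*

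**What the plan says.** Section 8.4 fixes the outcomes: "Clinical outcomes will be defined as the age of loss of ambulation, the age of introduction of cardiological supporting drugs", and, third, the age at which respiratory support began. It gives two ways to obtain them. The first is direct: "These ages will be directly obtained from the clinical reports (on report it is reported the age of the patient) of indirectly". The second, indirect, uses a report date: "according to the data of the report that describes the first introduction of the drug/devices or that firstly reports the loss of the ambulation" (I read 'data' there as 'date').

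The two routes feed one variable. The protocol does not ask for the route to be recorded, or for the date of the last report at which the milestone had not yet occurred. It does not say whether the directly obtained age is the age at the event or the age at the report.

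The ages matter to the primary aims. Section 8.1.1 lists "To identify any possible correlation between variables and clinical outcomes", and section 8.7.1 repeats the link to clinical outcomes. The charts may cover "visits and investigations performed through the years, also in other hospitals" (section 8.2.4). The only spacing mentioned is in section 8.5, "Only data corresponding to yearly visit (at least two data in two years) will be used for the linear correlation analysis", and that selects data for the correlation models; it does not date milestones. The limitations in section 8.9 do not mention dating error.

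**The concern.** Loss of ambulation usually happens between visits. The first chart to report it bounds the event from above, and the last chart without it bounds the event from below. Using the upper bound as the event age pushes the error in one direction, so it does not average out over patients. Its size depends on how densely each patient was charted.

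A natural history study exists largely to report ages such as these. If they are late, the disease looks slower than it is, even in a purely descriptive table and even if every patient is charted equally often. Treating patients who have not yet lost ambulation as right-censored is a separate matter and does not remove the lag in those who have. If the lower bound is not captured when the charts are read, no later analysis can recover it without reopening them.

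**Working it through.** The protocol gives no figure to reproduce: no chart gap, no SD and no share of ages dated by each route. The figure of 33 in section 8.5 is a head count of patients followed. What can be checked is how late a first-report date is under stated assumptions.

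**Inputs**
- Dating rule: section 8.4, indirect route.
- Gap between charts, g: not stated; assumed 0.5 to 3 years.
- Share of ages that are true event ages, d: not stated; taken as 0, 0.5 and 1.
- Event time: assumed uniform within the gap that contains it.

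**Step 1: regular gaps.** Mean lag = g/2; SD of the lag = g/√12. Lag over all ages = (1 − d) × g/2.

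| Gap g (years) | Mean lag, indirect ages | SD of lag | All ages, d = 0.5 | All ages, d = 1 |
|---|---|---|---|---|
| 0.5 | 0.25 | 0.14 | 0.125 | 0 |
| 1 | 0.50 | 0.29 | 0.25 | 0 |
| 2 | 1.00 | 0.58 | 0.50 | 0 |
| 3 | 1.50 | 0.87 | 0.75 | 0 |

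Simulation gave the same means for the indirect ages to within 0.001 year.

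**Step 2: irregular gaps.** A long gap is more likely to contain the event, so mean lag = E[G²] / (2E[G]). Three cases, all with a mean gap of 1 year:
- Gaps uniform from 0.5 to 1.5: E[G²] = 1 + 1/12 = 1.083, so the lag is 1.083/2 = 0.54 year.
- 80% of gaps 0.5 year and 20% 3 years: E[G] = 0.4 + 0.6 = 1.0; E[G²] = 0.2 + 1.8 = 2.0; lag = 2.0/2 = 1.00 year.
- Exponential gaps: E[G²] = 2, so the lag is 1.00 year.

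Half the average gap can thus understate the lag by up to about two-fold in these cases.

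**Step 3: which outcomes and routes.** The indirect rule has two limbs. For ambulation it is the first report of the loss, which need not carry the date of the loss; Steps 1 and 2 apply. For drugs and devices it is the report describing the first introduction. If that is the prescribing report, or it gives a start date, the lag is near zero; otherwise the same reasoning applies. On the direct route, an age at the event has no such lag, while an age at the report has the same lag as the indirect route.

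**Step 4: group comparison.** With every age dated indirectly, the false difference between groups with gaps g1 and g2 is (g2 − g1)/2: 0 for equal gaps, 0.5 year for 1 v 2, and 1.0 year for 1 v 3. For scale, with an assumed SD of 4 years and 33 patients split 16 v 17, the standard error of a difference is 4 × √(1/16 + 1/17) = 1.39 years.

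**Step 5: effect of recording both bounds.** For regular gaps, moving the date from the end of the interval to its midpoint changes the mean error from g/2 to g/2 − g/2 = 0. In simulation the midpoint bias stayed within 0.001 year.

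**The case against.** A reader might infer that all milestone ages are taken from the first chart and that all the clinical outcomes are late. Section 8.4 does not support that. The direct route is named first, the share of ages on each route is unknown, and if every age were a true event age the lag would be zero. For drugs and devices, section 8.3 also asks for therapy dates and for how long cardiac devices and wheelchairs have been used. These entries can supply start dates, and the wheelchair entry may help to date loss of ambulation.

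A reader might also infer that the lag creates a difference of about a year between genotype groups. That needs one group charted yearly, the other every three years, and every age dated indirectly. The documents show none of this. Genotype is the only split planned in section 8.7, and nothing suggests that chart density follows genotype. Collecting records from other hospitals adds dated reports and may shorten the gaps. Against the illustrative standard error of 1.39 years, a false difference of 0.5 to 1.0 year would also be smaller than sampling error.

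The choice of an interval-censored method could fairly be left to a statistical analysis plan, and dating an event to its first documentation is a usual convention in chart review. Both points limit the weight of the concern. They do not remove it: the protocol itself fixes the dating rule, and what is extracted from the charts determines whether a better analysis is possible.

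**Conclusion.** The point holds in a limited form. An age at loss of ambulation obtained indirectly is an upper bound and can only be late: by 0.25 to 1.5 years on average for assumed regular gaps of 0.5 to 3 years, and by more relative to the mean gap if charts are irregular. This applies to the indirectly dated ages alone, and the effect over the whole cohort shrinks in proportion to the share of true event ages. It reaches drugs and devices only where the report neither is the prescribing one nor gives a start date. It reaches the direct route only if the age read is the age at the report, which section 8.4 leaves open. Any bias between groups is conditional on unequal chart density and is not shown. All sizes in years rest on assumed gaps and a uniform event time. This is an inexpensive improvement to an outcome that feeds the primary endpoints; it does not call the study into question.

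**What to change.** In section 8.4, state that an age obtained directly means the age at the event. An age that is only the patient's age on the day of the report should be handled as indirect.

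For each milestone, add to the extraction file the route used, the date of the last report without the event and the date of the first report with it. Treat stated event ages as exact. Treat indirectly dated ages as interval-censored between the two reports, or as left-censored where no earlier report exists, using a Turnbull estimate or a parametric interval-censored model. Give the midpoint as a simple sensitivity analysis.

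The cost is a little more extraction work from charts that are already being read, and somewhat wider confidence intervals, because the uncertainty in the dates is then counted.
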